### Sample Size Calculation:

A priori power analysis for ANOVA, repeated measures, within-between interactions was used with an effect size of 0.28, alpha level ( $\alpha$ ) = 0.05, and power ( $1-\beta$ ) = 0.95. The estimated sample size required was 54 participants, which was increased to account for potential dropouts as shown in **(Figure 1)**. Thus, the total sample will include 60 participants, randomly allocated into 3 equal groups (n= 20 per group).

Sample size was calculated using G\*Power software version 3.1.9.7, referencing effect size data of pain severity from a recent study studying the effects of thoracic and hip joint mobility exercise with lumbar stabilization exercise on pain and balance **(Choi and Kim, 2023)**.

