**Figure (9): Hip Mobility Exercises. (Demirtas et al., 2023)**

### **Data analysis and statistical design**

Statistical analysis will be performed using SPSS software for Windows, version 25.0 (SPSS, Inc., Chicago, IL) with Alpha level set at 0.05.

- Data will be screened for normality assumption, homogeneity of variance, and presence of extreme scores.
- Descriptive statistics will be calculated for all groups at baseline and after 6 weeks.
- ANOVA, repeated measures, within-between interactions model will be utilized to determine any differences between the mean change scores of groups regarding all outcomes.
- Bonferroni adjusted p-values for every outcome measure to protect against the possibility of type I error.

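### Bonferroni is valid, but Holm gives the same familywise error control and never less power; the gain for thoracic versus hip ranges from about 1 to 11 points, depending on how the three means lie

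*Protocol*

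**What the plan says.** Under Data analysis and statistical design, the Protocol works "with Alpha level set at 0.05" and analyses every outcome with one model: "ANOVA, repeated measures, within-between interactions model will be utilized to determine any differences between the mean change scores of groups regarding all outcomes". The last bullet of that section fixes the adjustment: "Bonferroni adjusted p-values for every outcome measure to protect against the possibility of type I error". No stepwise or gated procedure is named, so ordinary single-step Bonferroni is the natural reading. The family is not stated. It could be the three group pairs within each outcome or the 11 null hypotheses listed under Hypotheses.

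The Sample Size Calculation section plans one interaction test "with an effect size of 0.28", alpha 0.05 and power 0.95, which needs 54 participants. Sixty will be "randomly allocated into 3 equal groups (n= 20 per group"). Outcomes are measured twice, at baseline and after 6 weeks. The Statement of the Problem asks which add-on is superior, thoracic or hip, and that is one of the three pairs.

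**The concern.** Single-step Bonferroni compares every p-value with 0.05 divided by the size of the family. Once one hypothesis has been rejected, fewer nulls can still be true, yet the divisor stays the same. Holm uses that slack. In a trial with 20 patients per arm and a pairwise question at its centre, the unused slack can mean missing a thoracic-versus-hip difference that an equally strict procedure would have found. The loss can be avoided without extra patients, provided the wording changes before the data are seen.

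**Working it through.** **Inputs from the Protocol.** Three arms, 20 each (18 each before the dropout allowance); two time points; alpha 0.05; f = 0.28; power 0.95; N = 54; 11 outcome hypotheses.

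**Assumptions, not in the text.** Pre-post correlation 0.5, two-sided tests, the patterns of means below, and correlation of 0 or 0.5 between outcomes.

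**1. The plan's own figure.** Noncentrality = f² × N × 2 / (1 − 0.5) = 0.28² × 54 × 4 = 16.93, with 2 and 51 degrees of freedom. Power is 0.956; N = 51 gives 0.944. So N = 54 reproduces, and N = 60 gives 0.973. With two time points the interaction test is a one-way F test on change scores, with f = 0.28 × √4 = 0.56. That corresponds to one arm differing by 0.56 × 3/√2 = 1.19 change-score SD, or to equally spaced means 0.56/√(2/3) = 0.69 SD apart.

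**2. Why Holm never loses.** Order the m p-values. Bonferroni compares all of them with 0.05/m. Holm compares the i-th smallest with 0.05/(m − i + 1) and stops at the first failure. Since 0.05/(m − i + 1) ≥ 0.05/m, every Bonferroni rejection is kept. For m = 3 the Holm limits are 0.0167, 0.025 and 0.05.

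**3. Pairs within one outcome.** Power for thoracic versus hip, 20 per arm, change SD 1, pooled variance, 200,000 simulated trials per row. The last column tests each pair at 0.05 only if the F test is significant at 0.05.

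| Means: control, hip, thoracic | Bonferroni | Holm | F-gated |
|---|---|---|---|
| 0, 0.69, 1.37 (design effect, middle contrast) | 0.39 | 0.50 | 0.57 |
| 0, 0.6, 1.2 | 0.29 | 0.38 | 0.46 |
| 0, 0.4, 1.2 | 0.53 | 0.61 | 0.69 |
| 0, 0, 1.19 (design effect, one arm differs) | 0.90 | 0.92 | 0.95 |
| 0, 0, 0.8 | 0.53 | 0.56 | 0.64 |
| 0, −0.69, 0.69 (design effect, widest contrast) | 0.967 | 0.969 | 0.973 |
| 0, −0.4, 0.4 | 0.53 | 0.54 | 0.57 |
| 0, −0.3, 0.3 | 0.29 | 0.30 | 0.34 |

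In the first three rows Holm gains 8 to 11 points and gating 16 to 18. When one arm differs, the gains are 2 to 3 and 5 to 11. When the pair is the widest, Holm gains 1 point or less and gating about 1 to 5. Beyond the design effect (0, 0.8, 1.6), Holm's gain reaches 13 points (0.53 to 0.66). With 18 per arm the first row becomes 0.35, 0.45 and 0.52.

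**4. Familywise error, common variance.** All means equal: 0.044 for Bonferroni and Holm, 0.050 for gating. Two arms equal and the third far away: 0.017 for Bonferroni, 0.049 for Holm and for gating.

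**5. Across the 11 outcomes.** Interaction test at 0.05/11, N = 60, design effect; average power per affected outcome, 20,000 simulated trials:

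| Outcomes affected | Bonferroni | Holm |
|---|---|---|
| 1 | 0.84 | 0.84 |
| 3 | 0.84 | 0.85 |
| 6 | 0.84 | 0.87 to 0.88 |
| 11 | 0.84 | 0.93 to 0.96 |

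Holm's familywise error stayed at 0.05 or below.

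**6. Unequal variances.** One arm far away with SD 1, the other two equal in mean, with SDs 1 and 1.5, 1 and 2, or 1.5 and 1.5 (illustrative; the Protocol gives none). With pooled-variance tests, the error for the true-null pair is 0.026, 0.034 and 0.029 under Bonferroni. It is 0.068, 0.082 and 0.075 under both Holm and gating. With unequal-variance pairwise tests, Holm returns to 0.050 in all three.

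**The case against.** The strongest reply is that nothing here is wrong: Bonferroni is valid, the choice among valid procedures is partly taste, and details of multiplicity can be left to an analysis plan. The first part stands, and this point claims only lost efficiency. But the Protocol does not leave the matter open. It names Bonferroni, and an alternative with the same guarantee and never less power exists.

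Bonferroni also gives matching simultaneous confidence intervals, which step-down tests do not. That stands and is a real, small cost.

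Bonferroni's slack also absorbed the error inflation in the unequal-variance cases of step 6, where Holm and gating with pooled tests exceeded 0.05. That stands as a condition. The inflation was the same for Holm and gating and vanished with unequal-variance tests, so it comes from the pooled p-values and not from stepping down.

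Four stronger readings might be inferred, and the documents do not support them:

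- **That the F-gated test dominates Bonferroni.** It does not. In up to about 0.5% of simulated trials Bonferroni rejected a pair while F was not significant. Only Holm dominates.
- **That thoracic versus hip is the weakest contrast.** All arms have 20 patients, so every pair has the same precision, and the Protocol gives no expected difference for any pair.
- **That the gain is large whatever happens.** It nearly disappears when thoracic and hip are the two extremes, or when only one to three outcomes respond.
- **That Bonferroni leaves type I error uncontrolled.** It does not.

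**Conclusion.** The point holds as an efficiency improvement. Under either reading of the family, Holm gives the same familywise control under the same assumptions and at least as many rejections. At 20 per arm and effects up to the design effect, it is worth about 8 to 11 points for thoracic versus hip as a middle contrast (up to about 18 with F-gating). It is worth about 1 point or less when that pair is the widest (1 to 5 with F-gating). Across outcomes it is worth about 9 to 12 points if all 11 are affected and almost nothing for one to three.

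That Holm never loses to Bonferroni is exact. The sizes rest on the assumed pre-post correlation, patterns of means and outcome correlations, and on normal data with a common variance.

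**What to change.** State the family, then replace the Bonferroni bullet with Holm-adjusted p-values for that family. Possible wording: 

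*For each outcome, the three pairwise comparisons of change form one family and are tested with Holm-adjusted p-values at a familywise level of 0.05.* 

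If the family is the outcomes, apply Holm to the 11 interaction p-values. If control over every pair and every outcome is meant, apply Holm to all 3 × 11 = 33 pairwise p-values.

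For the pairs within one outcome only, an acceptable and more powerful option is to test each pair at 0.05 after a significant group-by-time F test. With exactly three groups this is a closed test, given a common variance. It does not by itself cover several outcomes. If the planned homogeneity screen fails, use unequal-variance pairwise tests with Holm.

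Report Bonferroni simultaneous confidence intervals under their own label, with a note that they will not always agree with the step-down p-values. That mismatch is the only analytic cost; otherwise the change is a sentence or two of wording, made before the data are seen, with no extra patients or measurements.
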